8.2.7. Summary of Efficacy Analyses

Table 2. Summary of Efficacy Analyses

Endpoint	Analysis Set	Statistical Method	Objective
Change from baseline in YMRS total score at Week 4	ITT	MMRM	Primary Analysis
Change from baseline in YMRS total score at Week 4	PP	MMRM	Supportive of Primary Analysis
Change from baseline in YMRS total score at Week 4 – Sensitivity analysis (without 18 subjects)	ITT	MMRM	Sensitivity analysis of primary endpoint
Change from baseline in YMRS total score at Week 4 with interaction term of treatment and weight	ITT	MMRM	Sensitivity analysis of primary endpoint
Change from baseline in YMRS total score at Week 4 – Pattern Mixture Analyses	ITT	MMRM	Supportive of Primary Analysis
Change from baseline in YMRS total score at Week 4 – Pattern Mixture Analyses	PP	MMRM	Supportive of Primary Analysis
Change from baseline to week 4 in the CGI-S score	ITT	MMRM	Key-Secondary Analysis
Change from baseline to week 4 in the CGI-S score	PP	MMRM	Supportive of Key-Secondary Analysis
Change from baseline in YMRS total score and CGI-S score at Weeks 1, 2 and 3	ITT	MMRM	Secondary Analysis
Change from baseline in YMRS total score and CGI-S score at Weeks 1, 2 and 3	PP	MMRM	Supportive of Secondary Analysis
CGI-I score at weeks 1, 2, 3 and 4	ITT	MMRM	Secondary Analysis
CGI-I score at weeks 1, 2, 3 and 4	PP	MMRM	Supportive of Secondary Analysis
CCI			

Descriptive summaries are not included in this summary.

10. APPENDICES

Appendix 1. STATISTICAL METHODOLOGY DETAILS

[figure not shown]
Appendix 1.1. Sample SAS Code for the MMRM Analyses

Sample SAS code to fit the mixed model repeated measures specified in [Section 8.1.1](#) is given below. The response variable chg is the change from baseline at the study visits, Trtpn is the treatment group, avisitn is the assigned visit and blwcat is baseline weight category.

For the variance-covariance matrix: test various structures, start with the UN=unstructured matrix, in the case SAS PROC MIXED fails to converge, other covariance matrix structures will be considered in the sequence of Toeplitz, First-Order Autoregressive, and Variance Components/Covariance structure.

```
PROC MIXED DATA=xxxx EMPIRICAL;
  class trtpn avisitn blwcat usubjid;
  model chg = trtpn avisitn wtcat trtpn*avisitn base/ ddfm=kr2;
  repeated avisitn /subject= usubjid r type=UN rcorr covb;
  lsmeans trtpn*avisitn trtpn/ pdiff CL;
RUN;
ODS OUTPUT Diffs=diff
      LSMEANS = lsmeans;
Run;
```

CCI

Appendix 1.3. Sample SAS Code for the CGI-I Raw Scores MMRM Analyses

Sample SAS code to fit the MMRM model specified in 8.1.1 is given below, except there is no baseline in model. The response variable actual is the actual score at each study visit, Trtpn is the treatment group, avisitn is the assigned visit and blwcat is baseline weight category.

```
PROC MIXED DATA=xxxx EMPIRICAL;
  class trtpn avisitn blwcat usubjid;
  model actual = trtpn avisitn wtcat trtpn*avisitn / ddfm=kr2;
    repeated avisitn /subject= usubjid r type=UN rcorr covb;
    lsmeans trtpn*avisitn trtpn/ pdiff CL;
  RUN;
  ODS OUTPUT Diffs=diff
    LSMEANS = lsmeans;
  Run;
```

Appendix 1.4. Sample SAS Code for the Pattern Mixture Models Case 1 and Case 2

Description of variables:

The response variable chg is the change from baseline at the study visits, Trtpn is the treatment group, avisitn is the assigned visit and blwcat is baseline weight category.

Case 1: **dropout** variable defined as binary (0= All subjects who have YMRS score for Week 4, 1 = All subjects who do not have data at Week 4)

avgbase as average baseline value of all patients

pcomp1 as proportion completers in Ziprasidone (Number of completers in Zip/Total number of patients in Zip)

pdisc1 as proportion dropouts in Ziprasidone (Number of dropouts in Zip/Total number of patients in Zip)

pcomp2 as proportion completers in placebo

pdisc2 as proportion dropouts in placebo

pct_compldif as **pcomp1 - pcomp2**

pct_discdif as **pdisc1 - pdisc2**

Notes to the model below:

(1) The different estimates statements are used to illustrate how the construction of the last estimate statement ZIPRASIDONE vs PLACEBO Averaged over Patterns is done. Same for the difference of ZIPRASIDONE Averaged over Patterns and PLACEBO Averaged over Patterns.

(2) Case 1: As the dropout subgroup has no records on the last visit week 4, there are no corresponding coefficients, and these are hence ignored in estimate specification (in particular three-way interaction coefficients).

```

PROC MIXED DATA=xxxx EMPIRICAL;
  class avisitn trtpn usubjid blwcat dropout;
  model chg=blwcat base avisitn trtpn avisitn*trtpn
    dropout dropout*avisitn dropout*trtpn avisitn*trtpn*dropout / solution covb;
  repeated avisitn /subject= usubjid r type=UN;

estimate "ZIPRASIDONE in Completers"
intercept 1 base avgbase avisitn 0 0 0 1 trtpn 1 0 dropout 1 0 avisitn*trtpn 0 0 0 0 0 1 0
avisitn*dropout 0 0 0 0 0 1 0 trtpn*dropout 1 0 0 0 avisitn*trtpn*dropout 0 0 0 0 0 0 0 0 0
0 0 1 0 / cl singular=1;

estimate "ZIPRASIDONE in Discontinuations"
intercept 1 base avgbase avisitn 0 0 0 1 trtpn 1 0 dropout 0 1 avisitn*trtpn 0 0 0 0 0 1 0
trtpn*dropout 0 1 0 0 / cl singular=1;

estimate "ZIPRASIDONE Averaged over Patterns"
intercept 1 base avgbase avisitn 0 0 0 1 trtpn 1 0 dropout pcomp1 pdisc1 avisitn*trtpn 0 0 0
0 0 0 1 0 avisitn*dropout 0 0 0 0 0 pcomp1 0 trtpn*dropout pcomp1 pdisc1 0 0
avisitn*trtpn*dropout 0 0 0 0 0 0 0 0 0 pcomp1 0 0 0 / cl singular=1;

estimate "PLACEBO in Completers"
intercept 1 base avgbase avisitn 0 0 0 1 trtpn 0 1 dropout 1 0 avisitn*trtpn 0 0 0 0 0 0 1
avisitn*dropout 0 0 0 0 0 1 trtpn*dropout 0 0 1 0 avisitn*trtpn*dropout 0 0 0 0 0 0 0 0 0 0
0 0 1 0 / cl singular=1;

estimate "PLACEBO in Discontinuations"
intercept 1 base avgbase avisitn 0 0 0 1 trtpn 0 1 dropout 0 1 avisitn*trtpn 0 0 0 0 0 0 1
trtpn*dropout 0 0 0 1 / cl singular=1;

estimate "PLACEBO Averaged over Patterns"
intercept 1 base avgbase avisitn 0 0 0 1 trtpn 0 1 dropout pcomp2 pdisc2 avisitn*trtpn 0 0 0
0 0 0 0 1 avisitn*dropout 0 0 0 0 0 pcomp2 0 trtpn*dropout 0 0 pcomp2 pdisc2
avisitn*trtpn*dropout 0 0 0 0 0 0 0 0 0 0 pcomp2 0 0 / cl singular=1;

estimate "ZIPRASIDONE vs PLACEBO Averaged over Patterns"
trtpn 1 -1 dropout pct_compldif pct_discdif avisitn*trtpn 0 0 0 0 0 1 -1 avisitn*dropout 0
0 0 0 0 0 pct_compldif 0 trtpn*dropout pcomp1 pdisc1 -pcomp2 -pdisc2
avisitn*trtpn*dropout 0 0 0 0 0 0 0 0 0 0 pcomp1 -pcomp2 0 0 / cl singular=1;

ods output estimates=estimates1;

```

Case 2: dropout variable defined as binary (0= All subjects who have YMRS score for Week 3 or beyond, 1 = All subjects who do not have data beyond Week 2)

avgbase as average baseline value of all patients

pcomp1 as proportion completers in Ziprasidone (Number of completers in Zip/Total number of patients in Zip)

pdisc1 as proportion dropouts in Ziprasidone (Number of dropouts in Zip/Total number of patients in Zip)

pcomp2 as proportion completers in placebo

pdisc2 as proportion dropouts in placebo

pct_compldif as pcomp1 - pcomp2

pect **discdif** as **pdisc1** - **pdisc2**

Notes to the model below:

(1) The different estimates statements are used to illustrate how the construction of the last estimate statement ZIPRASIDONE vs PLACEBO Averaged over Patterns is done. Same for the difference of ZIPRASIDONE Averaged over Patterns and PLACEBO Averaged over Patterns.

Case 2: This code is very similar to case 1, except that the proportion of dropouts and completers will be different, also there will not be records for the last 2 visits in the dropout group, the week 3 related coefficients for dropouts will also not be available.

```

PROC MIXED DATA=xxxx EMPIRICAL;
  class avisitn trtpn usubjid blwcat dropout;
  model chg=blwcat base avisitn trtpn avisitn*trtpn
    dropout dropout*avisitn dropout*trtpn avisitn*trtpn*dropout / solution covb;
  repeated avisitn /subject= usubjid r type=UN;

estimate "ZIPRASIDONE in Completers"
intercept 1 base avgbase avisitn 0 0 0 1 trtpn 1 0 dropout 1 0 avisitn*trtpn 0 0 0 0 0 0 1 0
avisitn*dropout 0 0 0 0 0 1 trtpn*dropout 1 0 0 0 avisitn*trtpn*dropout 0 0 0 0 0 0 0 0 0 1 0
/ cl singular=1;

estimate "ZIPRASIDONE in Discontinuations"
intercept 1 base avgbase avisitn 0 0 0 1 trtpn 1 0 dropout 0 1 avisitn*trtpn 0 0 0 0 0 0 1 0
trtpn*dropout 0 1 0 0/ cl singular=1;

estimate "ZIPRASIDONE Averaged over Patterns"
intercept 1 base avgbase avisitn 0 0 0 1 trtpn 1 0 dropout pcomp1 pdisc1 avisitn*trtpn 0 0 0
0 0 0 1 0 avisitn*dropout 0 0 0 0 0 pcomp1 trtpn*dropout pcomp1 pdisc1 0 0
avisitn*trtpn*dropout 0 0 0 0 0 0 0 0 pcomp1 0/ cl singular=1;

estimate "PLACEBO in Completers"

```

intercept 1 base **avgbase** avisitn **0 0 0 1** trtpn **0 1** dropout **1 0** avisitn*trtpn **0 0 0 0 0 0 1** avisitn*dropout **0 0 0 0 0 1** trtpn*dropout **0 0 1 0** avisitn*trtpn*dropout **0 0 0 0 0 0 0 0 0 0** 1/ cl singular=1;

estimate "PLACEBO in Discontinuations"

intercept 1 base **avgbase** avisitn **0 0 0 1** trtpn **0 1** dropout **0 1** avisitn*trtpn **0 0 0 0 0 0 1** trtpn*dropout **0 0 0 1** / cl singular=1;

estimate "PLACEBO Averaged over Patterns"

```
intercept 1 base avgbase avisitn 0 0 0 1 trtpn 0 1 dropout pcomp2 pdisc2 avisitn*trtpn 0 0 0 0 1 avisitn*dropout 0 0 0 0 0 pcomp2 trtpn*dropout 0 0 pcomp2 pdisc2 avisitn*trtpn*dropout 0 0 0 0 0 0 0 0 0 pcomp2 / cl singular=1;
```

estimate "ZIPRASIDONE vs PLACEBO Averaged over Patterns"

```
trtpn 1 -1 dropout pct_compldif pct_disedif avisitn*trtpn 0 0 0 0 0 1 -1 avisitn*dropout 0 0 0 0 pct_compldif trtpn*dropout pcomp1 pdisc1 -pcomp2 -pdisc2 avisitn*trtpn*dropout 0 0 0 0 0 0 0 pcomp1 -pcomp2 / cl singular=1;
```

```
ods output estimates=estimates2;
```

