6.2. Visit 2 (Day 1) - Baseline

The baseline visit will occur 1-14 days after the screening visit, allowing time for wash-out of any antipsychotics and/or exclusionary medications and for laboratory results to be received and repeated, if necessary, to confirm eligibility. The following information/assessments will be collected /performed during the baseline visit:

- Confirm all inclusion/exclusion criteria are met.
- 12-lead triplicate ECG. See [Section 7.2.6](#).

- Blood pressure and pulse. See [Section 7.2.5](#).
- Laboratory evaluations only if clinically significant abnormalities are present at screening. Obtain blood and urine samples for blood chemistry, hematology, urinalysis, and hormones (free T4, TSH, and prolactin). See [Section 7.2.1](#).
- Fasting blood samples for glucose, lipid profile, insulin, HbA1c only if clinically significant abnormalities are present at screening. See [Section 7.2.1](#).
- For female subjects, a urine pregnancy test should be performed followed by a serum pregnancy test if the urine test is positive. A negative pregnancy test is required (at both the screening and baseline visits) before the subject may receive investigational product. See [Section 7.1](#).
- Urine sample for urine drug screen; see [Section 7.2.2](#).
- Efficacy assessments: YMRS, CGI-S, and CCI See [Section 7.3](#).
- CDRS-R. See [Section 7.2.7](#).
- C-SSRS. See [Section 7.2.9](#).
- Movement disorder scales: SARS, BAS, and AIMS. See [Section 7.2.8](#).
- Record concomitant medications.
- Assess and record any reported AEs.
- Randomization.
- Dispense study drug. Subjects will receive their first capsule in the afternoon/evening (with food) from the blister card PM column for Day 1.
- Contact should be made with the subject by the investigator or designated staff member, either by telephone or in person as an unscheduled visit, after the baseline visit but before Visit 3 to ensure that the subject is taking the proper capsules at the proper time and to monitor the tolerability, safety, and efficacy of the study drug.

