9.6.2. Analysis of Secondary Endpoints

The secondary efficacy endpoints include:

- Change from baseline to week 4 in the CGI-S score (key secondary endpoint);
- Change from baseline to weeks 1, 2, and 3 in YMRS and CGI-S;

- Raw CGI-I score at weeks 1, 2, 3, and 4 (as opposed to change from baseline).

For change from baseline in the CGI-S score, analyses will be conducted using SAS PROC MIXED to fit a mixed model repeated measures ANCOVA with treatment, visit and visit-by-treatment interaction and weight category as fixed effects and baseline score as a covariate. Subject effect will enter the MMRM model as a random effect.

For the raw CGI-I score, analyses will be conducted using SAS PROC MIXED to fit a mixed model repeated measures analysis of variance (ANOVA) with treatment, visit and visit-by-treatment interaction and weight category as fixed effects. Subject effect will enter the MMRM model as a random effect.

For all the above analyses, the estimation method used will be restricted maximum likelihood. An unstructured covariance matrix will be used in the REPEATED statement. In case SAS PROC MIXED fails to converge, other covariance matrix structures will be considered in the sequence of Toeplitz, First-Order Autoregressive and Variance Components. The EMPIRICAL option will be specified to compute the estimated variance-covariance matrix of the fixed-effects parameters. Type III sums of squares will be used to test both main effects and interactions. The point estimates and 95% CIs for the difference in means between the two treatments will be constructed using the least squares means and appropriate standard errors.

For all the above analyses, the point estimates and 95% CIs for the difference in means between the two treatments will be provided using the least squares means and appropriate standard errors.

Descriptive statistics for raw CGI-I scores and for change from baseline CGI-S scores will be provided by treatment group and visit classification.

CCI

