6.3. Covariates

Baseline values and weight category will be included as a covariate in the statistical models used to analyze endpoints requiring analysis of covariance (ANCOVA) by the protocol. See [Section 8](#) for details.

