8. STATISTICAL METHODOLOGY AND STATISTICAL ANALYSES

8.1. Statistical Methods

8.1.1. Mixed Model Repeated Measures Analyses (MMRM)

The endpoints including the primary, key-secondary, and secondary endpoints will be analyzed using a mixed model repeated measures analysis of covariance (MMRM); treatment, visit, visit-by-treatment interaction, and weight category as fixed effects and baseline score (with the exception of CGI-I score) as a covariate. Subject effect will enter the MMRM model as a random effect. The estimation method used will be restricted maximum likelihood. An unstructured covariance matrix will be used in the REPEATED statement. In case SAS PROC MIXED fails to converge, other covariance matrix structures will be considered in the sequence of Toeplitz, First-Order Autoregressive, and Variance Components. The EMPIRICAL option will be specified to compute the estimated variance-covariance matrix of the fixed-effects parameters. Type III sums of squares will be used to test both main effects and interactions.

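### The CGI-I model has no baseline severity term; baseline CGI-S is already collected and could be added at negligible cost, for a gain the documents do not let us size

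*SAP*

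**What the plan says.** Three places describe the CGI-I model, and they agree.

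- Protocol 9.6.2 analyses the raw CGI-I score with a "mixed model repeated measures analysis of variance (ANOVA) with treatment, visit and visit-by-treatment interaction and weight category as fixed effects". No baseline covariate is listed.
- SAP 8.1.1 gives the primary, key secondary and secondary endpoints one common model, with "baseline score (with the exception of CGI-I score) as a covariate".
- SAP Appendix 1.3 carries this into code, "except there is no baseline in model". The statement reads "model actual = trtpn avisitn wtcat trtpn*avisitn / ddfm=kr2".

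The YMRS and CGI-S models in Protocol 9.6.1 and 9.6.2 and in SAP 8.1.1 do include the baseline score. So do the YMRS pattern-mixture models in SAP 8.2.1.

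CGI-S is scheduled at screening and baseline (Protocol, Schedule of Activities). The baseline visit procedures list it: "Efficacy assessments: YMRS, CGI-S, and CCI". SAP 5.1 requires baseline measurements for membership of the ITT set. Protocol 7.3.2 describes CGI-S and CGI-I as two subscales of one instrument, with CGI-I rated relative to the subject's baseline state.

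**The concern.** CGI-I has no baseline value of its own, which is the evident reason for leaving baseline out. The visible text does not say why that should mean no severity adjustment at all, when the companion severity rating is taken at the baseline visit.

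Two things are at stake, both modest. The first is precision and chance imbalance. Randomization is stratified by weight group only, so the arms can differ by chance in baseline severity, and the CGI-I estimate would not correct for it.

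The second is missing data. The re-estimated dropout is about 20% (SAP 2.2.1), and insufficient response is a route to withdrawal (Protocol 3 and 6.7.1). The repeated-measures model relies on data being missing at random given what it conditions on. For YMRS and CGI-S that includes baseline severity. For CGI-I it is only treatment, weight category and the CGI-I scores observed so far, which is a single score for a subject who leaves after Week 1. Conditioning on baseline CGI-S as well would make the assumption somewhat more plausible.

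**Working it through.** **The plan's own figures.** The documents give no effect size, standard deviation, power or sample size for CGI-I. Their sizing is for YMRS: difference 4.55, SD 8.0, two-sided 5%, power 85%. Total N = 4 x [8.0 x (1.960 + 1.036) / 4.55]^2 = 111.0, which reproduces the stated 111. Then 111 / 0.80 = 138.75 (stated as about 138), and 138 + 18 = 156. These figures say nothing about CGI-I precision. They supply only the number of subjects.

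**Inputs for the check.**
- Planned total 156 and dropout of about 20% (SAP 2.2.1), so 156 x 0.80 = 124.8, or about 125 subjects with Week 4 data.
- r, the within-arm correlation of baseline CGI-S with post-baseline CGI-I. It is not in the documents and is assumed here to lie between 0 and 0.4.

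**Formulas.**
- Variance after adjustment / variance before = 1 - r^2.
- Equivalent extra subjects = 125 x [1/(1 - r^2) - 1].
- Net SE ratio, allowing for estimation of one slope = sqrt[(1 - r^2) x (1 + 1/(N - 4))]. With N = 125 the slope factor is 1 + 1/121 = 1.0083.

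| Assumed r | Variance reduction | Equivalent extra subjects | Net SE ratio |
|---|---|---|---|
| 0 | 0% | 0 | 1.004 |
| 0.1 | 1% | 125 x 0.0101 = 1.3 | 0.999 |
| 0.2 | 4% | 125 x 0.0417 = 5.2 | 0.984 |
| 0.3 | 9% | 125 x 0.0989 = 12.4 | 0.958 |
| 0.4 | 16% | 125 x 0.1905 = 23.8 | 0.920 |

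At r = 0 the SE is 0.4% larger with N = 125. With N = 111 it is sqrt(1 + 1/107) = 1.005, or 0.5% larger. Break-even with N = 125 is where 1 - r^2 = 121/122, that is r = sqrt(1/122) = 0.09.

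**In terms of power.** Suppose, purely for illustration, that unadjusted power for CGI-I is 80%. Adjusted power is then Phi[(1.960 + 0.842)/sqrt(1 - r^2) - 1.960]. This gives 80.4% at r = 0.1, 81.6% at r = 0.2 and 83.6% at r = 0.3.

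These formulas describe one visit with complete data. In the repeated-measures model, with a single slope shared across visits, they are approximations.

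**The case against.** The case for leaving the model alone is a serious one.

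- **No inconsistency.** Protocol and SAP specify the same model in three places. A reader might infer from the opening of SAP 6.3 that a baseline covariate was required for CGI-I too. It was not: that section is limited to "endpoints requiring analysis of covariance (ANCOVA) by the protocol", and the protocol assigns CGI-I to ANOVA. SAP 6.3 lends the point no support.
- **CGI-I already refers to baseline.** It rates change since baseline, so its correlation with baseline severity may be small. The entry threshold of YMRS 17 or more at both screening and baseline narrows the severity range and may reduce r further. A reader might take it as fact that the plan loses precision. Without r, that is not shown.
- **No bias from chance imbalance.** Under randomization, imbalance in baseline CGI-S is part of the unadjusted standard error and does not bias the estimate.
- **The missing-data gain is theoretical.** Observed CGI-I already tracks the insufficient response that leads to withdrawal. Nothing shows that baseline severity predicts dropout once observed CGI-I is taken into account.
- **Not a unique exception, as far as can be checked.** A reader might infer that every other efficacy model adjusts for baseline. Parts of SAP 8.2.3, Table 2 and the appendices are redacted, so only the visible models can be compared.

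All of this stands, and it reduces the point to an optional improvement. What remains is that a closely related covariate is already scheduled for every randomized subject, the worst case is an SE about 0.5% larger, and the possible benefit is larger than that once r exceeds about 0.1.

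**Conclusion.** This is a minor, optional efficiency improvement and not a flaw in the plan. The CGI-I model is deliberately and consistently unadjusted, and its treatment comparison is unbiased under randomization apart from missing data. Adding baseline CGI-S would reduce variance by about r^2: between nothing and 16% for r from 0 to 0.4, a range that is assumed because the documents give no value. It would also remove chance imbalance in baseline severity from the estimate and let the missing-at-random assumption condition on it.

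The consequence is confined to CGI-I. Under SAP 4.2 the efficacy conclusion rests on YMRS, and only the key secondary CGI-S is tested conditionally on it. Both of those models already adjust for baseline. No stated decision rule depends on CGI-I.

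That baseline CGI-S will be present for every analysed subject is what the schedule and the ITT definition plan for. It is not an observed fact. A subject lacking it would drop out of the adjusted CGI-I model, just as that subject already would from the CGI-S model.

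**What to change.** Before unblinding, amend SAP 8.1.1 so that the CGI-I model takes baseline CGI-S as its covariate, and add that single term to the MODEL statement in Appendix 1.3, leaving the other terms as they are. Align Protocol 9.6.2 at the next amendment. Protocol 9.2 allows the SAP to modify the protocol's analysis plans and calls for a protocol amendment only for major modifications or significant changes to the primary endpoint or its analysis, so the SAP edit can go first. If the sponsor prefers to keep the present model as the main CGI-I analysis, the adjusted model could be pre-specified as a sensitivity analysis.

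The cost is one model term and one degree of freedom, with no new data collection and no effect on the primary or key secondary analysis.

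As a separate coding matter, the Appendix 1.3 code names the weight variable blwcat in the CLASS statement and wtcat in the MODEL statement. The two should be reconciled when the line is edited.

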8.2. Statistical Analyses

8.2.1. Primary Analysis

The primary efficacy endpoint is change from baseline in the YMRS score. The primary time point is Week 4. The primary endpoint will be analyzed using the MMRM model described in [Section 8.1.1](#). The primary comparison will be between ziprasidone and placebo at Week 4, conducted as a two-sided test at 5% level of significance. Based on the specified model, the point estimate and 95% confidence interval (CI) for the difference in means between the two treatments will be constructed using the least squares means and appropriate standard errors.

If the test result is significant (p-value ≤ 0.05) and in favor of ziprasidone, then efficacy of flexibly-dosed oral ziprasidone in the treatment of children and adolescents with Bipolar I Disorder (current or most recent episode manic) will be established.

A sensitivity analysis will be done by adding an interaction term of treatment and weight category to the primary analysis model specified in [Section 8.1.1](#).

Supplemental analyses of the primary variable will be performed to support the robustness of the conclusions drawn from the primary mixed models repeated measures analysis described above. These supplemental analyses will include the following:

- Summaries of reasons for discontinuations by treatment group;
- Pattern-mixture ANCOVA analysis of change from baseline YMRS scores.

For the pattern-mixture analysis, grouping of the subjects on the basis of their dropout or missing-data patterns will be explored. ‘Patterns’ will be defined under the following two cases:

Case 1:

Pattern 1A - all subjects who have completed the study

Pattern 1B - all subjects who have discontinued the study

Case 2:

Pattern 2A - all subjects who have YMRS score for Week 3 or beyond.

Pattern 2B - all subjects who do not have data beyond Week 2.

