A mixed effects repeated measures analysis of covariance model will be used to analyze change from baseline in YMRS score under each of the above cases. These models will include terms for treatment, pattern (as defined above), weight category, treatment-by-pattern interaction, visit, treatment by visit interaction, and visit by pattern interaction as fixed effects, baseline as a covariate, and subject as random effect. The estimation method used will be restricted maximum likelihood. The covariance structure among repeated measures will be assumed to be adequately modeled using an unstructured matrix. In case SAS PROC MIXED fails to converge, other covariance matrix structures will be considered in the sequence of Toeplitz, First-Order Autoregressive, and Variance Components. The EMPIRICAL option (in SAS) will be specified to compute the estimated variance-covariance matrix of the fixed-effects parameters. Type III sums of squares will be used to test both main effects and interactions. The primary comparison will be between ziprasidone and placebo at Week 4, averaged over the missing data patterns, and conducted as a two-sided test at 5% level of significance. Based on the specified model, the point estimate and 95% confidence interval (CI) for the difference in means between the two treatments will be constructed using the least squares means and appropriate standard errors.

The percentage of subjects showing a ≥50% reduction in YMRS scores from baseline to Week 4 will be presented descriptively for each group. Additionally, descriptive statistics for change from baseline in YMRS score will be provided by treatment group and visit classification.

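### SAP Appendix 1.4: the pattern-averaged Week 4 contrast is not estimable as coded, rests on an unstated assumption about dropouts, and does not match Section 8.2.1

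*SAP*

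**What the plan says.** SAP Section 8.2.1 plans a pattern-mixture analysis of YMRS change under two groupings, and Table 2 lists it as supportive of the primary analysis.

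- **Model in the text.** Beyond the main effects, Section 8.2.1 lists "treatment-by-pattern interaction, visit, treatment by visit interaction, and visit by pattern interaction as fixed effects". It has no three-way term. The Week 4 comparison is to be "averaged over the missing data patterns, and conducted as a two-sided test at 5% level of significance"; whether the weights are pooled or by arm is not said.
- **Model in the code.** The MODEL statement in Appendix 1.4 includes "dropout dropout*avisitn dropout*trtpn avisitn*trtpn*dropout / solution covb", so a three-way term is fitted.
- **Case 1 in the text.** "Pattern 1B - all subjects who have discontinued the study".
- **Case 1 in the code.** The dropout indicator is "1 = All subjects who do not have data at Week 4".
- **Case 2.** Text and code agree: dropouts have no data beyond Week 2.
- **Weights in the code.** The final contrast uses each arm's own completer and dropout proportions: "trtpn*dropout pcomp1 pdisc1 -pcomp2 -pdisc2".
- **Empty cells.** The Case 1 note reads "As the dropout subgroup has no records on the last visit week 4, there are no corresponding coefficients, and these are hence ignored". The Case 2 note says the same of Weeks 3 and 4.
- **Tolerance.** Every ESTIMATE statement carries the option seen in "trtpn*dropout 0 1 0 0 / cl singular=1".

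**The concern.** A three-way model gives every visit-by-arm-by-pattern cell its own mean. Under the code's patterns nobody in the dropout group is observed at Week 4, so the data say nothing about that mean. Leaving its coefficients out of the ESTIMATE statement does not take the mean out of the target, because the dropout weight is still there. If the check is relaxed, software will probably print a figure anyway, and that figure is set by how the model is parameterised.

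This is the only modelled missing-data supplement shown in SAP Table 2, and its purpose is to show that the MMRM conclusion is robust to dropout. Its assumption about dropouts should therefore be visible. In addition, an analyst following Section 8.2.1 and one following Appendix 1.4 would fit different models, possibly on different patterns.

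**Working it through.** The plan gives no numerical result for this analysis, so there is none to reproduce.

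**Inputs.** Four post-baseline visits, two arms and two patterns (SAP 8.2.1, Appendix 1.4). Dropout is about 20% overall (SAP 2.2.1), with no split by arm. The splits 19/21 and 15/25 (% ziprasidone/placebo) are assumptions around 20%. The split 35/42 follows from the 65% and 58% completion in study A1281132 (Protocol 1.2.2.1.2). Write p1, p2 for the dropout proportions in ziprasidone and placebo, and D for the completer difference at Week 4.

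**1. Test.** A contrast is estimable if it lies in the row space of the design matrix. Empty cells were left out: 14 of 16 cells are observed under the code's Case 1, and 12 under Case 2. Under the text's Case 1 there are 15 if one arm has a discontinuer with a Week 4 rating, and 16 if both arms do.

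| Model and pattern | 20/20 | 19/21 | 15/25 | 35/42 |
|---|---|---|---|---|
| Three-way, code's Case 1 or Case 2 | no | no | no | no |
| Two-way, code's Case 1 or Case 2 | yes | no | no | no |
| Two-way, text's Case 1, Week 4 discontinuer in one arm | yes | yes | yes | yes |
| Three-way, text's Case 1, Week 4 discontinuer in one arm | no | no | no | no |
| Three-way, text's Case 1, Week 4 discontinuer in both arms | yes | yes | yes | yes |

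**2. Three-way model, code's patterns.** Contrast = D + p1 × gap1 − p2 × gap2, where each gap is that arm's dropout-minus-completer difference at Week 4. Neither gap is observed. A 1-point change in one gap moves the contrast by that arm's p: 0.20 points at 20% dropout, 0.38 at the original 38%.

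**3. What a forced solution assumes.** The model was solved in the coded order, visits 1 to 4, setting later dependent columns to zero, on random cell means (three draws per Case, both arms). The dropout Week 4 mean always equalled the completer Week 4 mean plus that arm's gap at the last dropout visit: Week 3 in Case 1, Week 2 in Case 2.

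An illustration with assumed Case 1 means: completers go from −13 (Week 3) to −15 (Week 4) on ziprasidone and from −9 to −10 on placebo; dropouts at Week 3 are −1 and −4.

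- Gaps: −1 − (−13) = 12 and −4 − (−9) = 5.
- Implied dropout Week 4 means: −15 + 12 = −3 and −10 + 5 = −5.
- Contrast at 20/20: [0.8(−15) + 0.2(−3)] − [0.8(−10) + 0.2(−5)] = −12.6 + 9.0 = −3.6.
- Same data with visits in descending order: implied dropout means −13 and −8, contrast −14.6 + 9.6 = −5.0.
- Same data with the three-way term listed first and ziprasidone as the first treatment level: implied means −10 and −10, contrast −14.0 + 10.0 = −4.0.

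**4. Two-way model, code's patterns.** Write the dropout gap as g(visit) + h(arm). Then contrast = D + p1 × h1 − p2 × h2 + (p1 − p2) × g(4), and g(4) is never observed. It cancels only when p1 = p2. At 20/20, with equal cell weights, the contrast in Case 1 is D + 0.20 × the Weeks 1-3 average of (dropout treatment difference − completer treatment difference). That carries the treatment-by-pattern effect forward unchanged to Week 4. With arm-specific weights, the undetermined part per point of g(4) is |p1 − p2|: 0.02 at 19/21, 0.10 at 15/25 and 0.07 at 35/42.

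**5. Arm-level rows.** In every design row the intercept equals the sum of the two weight-category indicators. An estimable function with intercept 1 therefore needs `blwcat` coefficients summing to 1. The arm-level ESTIMATE statements have intercept 1 and no `blwcat` coefficients, so none is estimable as printed, completer rows included. With the code's patterns, adding them rescues only the completer rows. The between-arm contrast has intercept 0, so this defect does not touch it.

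**6. Text against code on Case 1.** Protocol 6.7 asks for all Week 4 assessments at early termination, and SAP Appendix 2 slots Days 25-31 to Week 4. A discontinuer rated then is Pattern 1B in the text but a non-dropout in the code. A study completer with no Week 4 score is the reverse.

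**The case against.** The code is headed as sample code, Section 8.2.1 says the grouping will be explored, and the notes openly say that dropouts lack late records and that the coefficients are dropped. That is fair: nothing is hidden. But the notes do not say what dropping the coefficients assumes about outcomes, and the appendix is the only place that gives the contrast and its weights.

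The sizes are largely assumed. This stands: no split by arm is given, and at 19/21 the undetermined part of the two-way contrast is small.

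Four stronger readings are tempting, and the documents do not support them.

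- A reader might infer that Section 8.2.1's two-way model cures the problem. With the code's patterns it is estimable only at common weights, and only by holding the treatment-by-pattern effect constant over visits.
- A reader might infer that the two Case 1 definitions must give different answers. They differ only for subjects such as discontinuers rated on Days 25-31; that number is not given and may be zero. Conversely, if one such subject makes the contrast formally estimable, that subject carries the whole Week 4 pattern effect.
- A reader might count coefficients in the printed ESTIMATE rows and call them misplaced. Those counts may be broken by PDF reading, so the check used the intended contrast.
- A reader might infer that the efficacy claim is at risk. It is not: under SAP 4.2 it depends on the primary MMRM.

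**Conclusion.** The point holds for the supportive analysis. As coded, the averaged Week 4 contrast is not estimable in either Case at any split tested, and `singular=1` makes it likely that a parameterisation-dependent number is printed without warning. In the coded order that number assumes that the last observed dropout-completer gap persists in each arm. Text and code also disagree on the model terms and on the Case 1 pattern.

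The sensitivity is 0.20 YMRS points per point of one arm's gap at 20% dropout under the three-way model. Under the two-way model with arm-specific weights it is 0.02 to 0.10 per point of the common Week 4 gap, over the unequal splits examined. The estimability results rest on the code's empty cells; the splits and the illustrative means are assumptions. The primary MMRM estimate, test and interval, the decision rule and the key secondary endpoint are unaffected. This should be fixed, preferably before unblinding, so that the choice between the two specifications is not made with results in hand.

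**What to change.** 1. Use one model and one Case 1 definition in both Section 8.2.1 and Appendix 1.4, and say how a discontinuer with a slotted Week 4 rating is classified.
2. Remove `singular=1` as a way around the estimability check.
3. Under whichever model is kept, state the identifying assumption for dropouts at Week 4 and build it into the ESTIMATE coefficients. For the three-way model this could be that the last observed dropout-completer gap persists in each arm; for the two-way model it is that the treatment-by-pattern effect is constant over visits.
4. State whether pattern weights are pooled or by arm. If pooled weights are used with the two-way model, say that the estimand no longer reflects each arm's own pattern mix. If arm-specific weights are kept with it, add an explicit restriction for the common Week 4 gap.
5. Add `blwcat` coefficients to any arm-level estimate that is kept, and drop arm-level estimates that remain non-estimable.

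The cost is SAP wording and sample code. No new data and no protocol change are needed.
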